A Pilot Randomized Controlled Trial to Evaluate an Advanced Borderless Dressing (ALLEVYN™ LIFE Non-Bordered) in the Treatment of Chronic Ulcers	

1. List of Abbreviations

Abbreviation	Definition
ADE	Adverse Device Effect(s)
ADL	Activities of Daily Living
AE	Adverse Event(s)
ALNB	ALLEVYN™ LIFE Non-Bordered
ANOVA	Analysis of Variance
ANCOVA	Analysis of Co-Variance
BMI	Body Mass Index
CRF	Case Report Form(s)
CWIS	Cardiff Wound Impact Schedule
DevD	Device Deficiency(ies)
DFU	Diabetic Foot Ulcer
EQ-5D	EuroQol 5D
FAS	Full Analysis Set
GQ	Global Quality of life
HCP	Healthcare Professional
HRQoL	Health Related Quality of Life
LOCF	Last Observation Carried Forward
LU	Leg Ulcer
MedDRA	Medical Drug Regulatory Activities
PSDL	Physical Symptoms of Daily Living
PP	Per-protocol Population
PU	Pressure Ulcer
QoL	Quality of Life
S&N	Smith & Nephew Inc.
SADE	Serious Adverse Device Effect(s)
SAE	Serious Adverse Event(s)
SAP	Statistical Analysis Plan

CONFIDENTIAL AND PROPRIETARY

This document contains information that is confidential and proprietary to Smith & Nephew PLC and Smith & Nephew, Inc. and is intended for use only by Smith & Nephew and its manufacturer. It shall not be reproduced or copied in whole or in part, nor shall the contents be disclosed by any means without prior written permission from Smith & Nephew, nor shall anyone make any use of it that is contrary to the expressed or implied wishes of Smith & Nephew

Statistical Analysis Plan	 smith&nephew
A Pilot Randomized Controlled Trial to Evaluate an Advanced Borderless Dressing (ALLEVYN™ LIFE Non-Bordered) in the Treatment of Chronic Ulcers	Number: CT1603ALF
	ST: 1005
	Version: 1.0, 27-Jul-2018
	Page: 6 of 27

Abbreviation	Definition
SAF	Safety Population
SC	Standard Care
SL	Social Life
SQ	Satisfaction with quality of life
TFL	Tables, Figures and Listing
USADE	Unanticipated Serious Adverse Device Effect(s)
VLU	Venous Leg Ulcer
WB	Well-being

CONFIDENTIAL AND PROPRIETARY

This document contains information that is confidential and proprietary to Smith & Nephew PLC and Smith & Nephew, Inc. and is intended for use only by Smith & Nephew and its manufacturer. It shall not be reproduced or copied in whole or in part, nor shall the contents be disclosed by any means without prior written permission from Smith & Nephew, nor shall anyone make any use of it that is contrary to the expressed or implied wishes of Smith & Nephew

Statistical Analysis Plan	 Number: CT1603ALF
A Pilot Randomized Controlled Trial to Evaluate an Advanced Borderless Dressing (ALLEVYN™ LIFE Non-Bordered) in the Treatment of Chronic Ulcers	ST: 1005
	Version: 1.0, 27-Jul-2018
	Page: 7 of 27

[figure not shown]
2. Introduction

The following Statistical Analysis Plan (SAP) details the statistical considerations, including the data analysis methods, for the Study Protocol CT1603ALF. Related documents to this SAP are the Study Protocol, Case Report Form (CRF), and Tables, Figures and Listings (TFLs) Shells.

3. Study Design

This is a stratified, randomized, parallel group study. Subjects will be randomly assigned to ALLEVYN™ LIFE Non-Bordered (ALNB) or Standard Care (SC) respectively in a 5:3 ratio. Subjects will be stratified by ulcer type: diabetic foot ulcer (DFU), leg ulcer (LU) and pressure ulcer (PU). Participation in the study will last up to 12 weeks. Subjects will be required to make at least one visit per week to the research site. The primary clinical endpoint will be six (6) weeks from enrollment, with clinical data also collected at three (3) and twelve (12) week follow-up visits. Health care resource use data will be gathered and compared over the entire twelve week study period. Figure 3.1 below shows an overview of the study design and table 3.1 shows the planned visit schedule.

Figure 3.1 – Overview of Study Design

CONFIDENTIAL AND PROPRIETARY

This document contains information that is confidential and proprietary to Smith & Nephew PLC and Smith & Nephew, Inc. and is intended for use only by Smith & Nephew and its manufacturer. It shall not be reproduced or copied in whole or in part, nor shall the contents be disclosed by any means without prior written permission from Smith & Nephew, nor shall anyone make any use of it that is contrary to the expressed or implied wishes of Smith & Nephew.

Statistical Analysis Plan	 smith&nephew
A Pilot Randomized Controlled Trial to Evaluate an Advanced Borderless Dressing (ALLEVYN™ LIFE Non-Bordered) in the Treatment of Chronic Ulcers	Number: CT1603ALF ST: 1005 Version: 1.0, 27-Jul-2018 Page: 8 of 27

Table 3.1: Study Visit Schedule

Procedure	Key Visits			Other Visits	
	Visit 1 (Baseline)	Visit 2 (Day 21±3) and Visit 3 (Day 42±4)	End of Study Visit (Day 84±4)	Routine Dressing Changes	Treatment D/C (before end of study)
Informed Consent	√				
Demographics/Medical History	√				
Concomitant Medication	√	√	√	√	√
CWIS	√	√	√		√
Ulcer Assessment	√	√	√	√	√
ABI	√ ¹				
Verify Inclusion/Exclusion	√				
Allocate Study ID Number	√				
Randomize	√				
Photograph Ulcer	√	√	√	√ ²	√
Photograph Dressing	√ ³	√	√	√ ³	√ ³
Dressing Change		√		√	
Complete Questions about Dressing (Subject and Investigator)	√	√	√	√	√
Pain scale		√	√	√	
Record Adverse Events (AE)	√	√	√	√	√
Record Device Deficiencies (DevD)	√	√	√	√	√
Complete Exit Form			√		

¹ If not obtained within last 30 days for DFU/LU subjects

² Only if AE related to ulcer is observed

³ Only if DevD observed

4. Study Objectives

The overall aim of this pilot randomized controlled trial is to gather preliminary clinical, health economic and safety data on the use of ALNB in the treatment of chronic wounds, for postmarket surveillance and to assist with planning future research concerned with the efficacy and cost-effectiveness of ALNB. The specific objectives are subsequently described.

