#### Healthcare resource use

The following Healthcare resource variables will be summarized by treatment groups and overall at twelve weeks:

- Number and type of dressings used (both primary and secondary dressings), including use of compression therapy
- Number of outpatient visits
- Amount of time in hospital (nights spent as an inpatient)
- Number and type of interventions/procedures including debridement of ulcer (curette, scissors, scalpel, forceps, other)
- Number and type of concomitant therapies/treatments

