4.3 Secondary Objectives

Secondary objectives of this study are:

- Ulcer progression (including undermining, necrotic tissue type and amount, exudate type and amount, skin color surrounding the wound, granulation tissue, epithelialization, condition of peri-wound, ulcer dimensions and healing status) at three, six, and twelve weeks
- Healthcare resource use related to the reference ulcer (including number and cost of dressings used, consultations and time used by healthcare professionals (HCP), time in hospital, number and cost of additional treatments, procedures, and investigations) over twelve weeks

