5.3 Secondary Endpoints

Ulcer progression variables to be compared between groups at three, six, and twelve weeks including:

- Modified Bates-Jensen Wound Assessment Tool
 - Undermining
 - Necrotic tissue type
 - Necrotic tissue amount
 - Exudate type

CONFIDENTIAL AND PROPRIETARY

This document contains information that is confidential and proprietary to Smith & Nephew PLC and Smith & Nephew, Inc. and is intended for use only by Smith & Nephew and its manufacturer. It shall not be reproduced or copied in whole or in part, nor shall the contents be disclosed by any means without prior written permission from Smith & Nephew, nor shall anyone make any use of it that is contrary to the expressed or implied wishes of Smith & Nephew

Statistical Analysis Plan	
A Pilot Randomized Controlled Trial to Evaluate an Advanced Borderless Dressing (ALLEVYN™ LIFE Non-Bordered) in the Treatment of Chronic Ulcers	Number: CT1603ALF
	ST: 1005
	Version: 1.0, 27-Jul-2018
	Page: 11 of 27

- Exudate amount
- Skin color surrounding the wound
- Granulation tissue
- Epithelialization
- Condition of peri-wound
- Ulcer dimensions
- Ulcer healed status

Healthcare resource use variables (to be compared between groups over the entire twelve week study period) including:

- Dressings used (number and type for both primary and secondary dressings), including use of compression therapy
- Healthcare consultations (number and type)
- Time spent by health care providers (HCP) in treating/caring for reference ulcer
- Time in hospital (nights spent as an inpatient due to reference ulcer)
- Interventions/procedures related to the reference ulcer (number and type), including debridement of the ulcer (curette, scissors, scalpel, forceps, other)
- Concomitant therapies/treatments (number and type) used on the reference ulcer

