7.1 General

Smith & Nephew's Global Biostatistics group will conduct the statistical analysis for this study. Unless otherwise stated, all significance tests and hypothesis testing will be two-sided, performed at the 5% significance level. Resulting p-values will be quoted and 95% two-sided confidence intervals will be generated where appropriate. All p-values will be

CONFIDENTIAL AND PROPRIETARY

This document contains information that is confidential and proprietary to Smith & Nephew PLC and Smith & Nephew, Inc. and is intended for use only by Smith & Nephew and its manufacturer. It shall not be reproduced or copied in whole or in part, nor shall the contents be disclosed by any means without prior written permission from Smith & Nephew, nor shall anyone make any use of it that is contrary to the expressed or implied wishes of Smith & Nephew

Statistical Analysis Plan	 Number: CT1603ALF ST: 1005 Version: 1.0, 27-Jul-2018 Page: 13 of 27
A Pilot Randomized Controlled Trial to Evaluate an Advanced Borderless Dressing (ALLEVYN™ LIFE Non-Bordered) in the Treatment of Chronic Ulcers	

rounded to three decimal places, p-values less than 0.001 will be presented as ‘<0.001’ in all tables.

Where data summaries are specified, categorical and ordinal variables will be summarized with frequencies and percentages. Continuous variables will be summarized with the following summary statistics: number of observations, mean, median, standard deviation, minimum and maximum values. All analyses will be performed in SAS 9.4 (or later).

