If a subject has missing data for any values for length, width or depth of the wound at a particular visit, and has at least one post-baseline score, then the LOCF method will be used. The only exception to this is when missing values occur and the ulcer is healed, in which case 0cm (length/ width) or 0mm (depth) shall be imputed for all missing measurements in the statistical analysis.

Ulcer healed status

CONFIDENTIAL AND PROPRIETARY

This document contains information that is confidential and proprietary to Smith & Nephew PLC and Smith & Nephew, Inc. and is intended for use only by Smith & Nephew and its manufacturer. It shall not be reproduced or copied in whole or in part, nor shall the contents be disclosed by any means without prior written permission from Smith & Nephew, nor shall anyone make any use of it that is contrary to the expressed or implied wishes of Smith & Nephew

Statistical Analysis Plan	 Number: CT1603ALF ST: 1005 Version: 1.0, 27-Jul-2018 Page: 15 of 27
A Pilot Randomized Controlled Trial to Evaluate an Advanced Borderless Dressing (ALLEVYN™ LIFE Non-Bordered) in the Treatment of Chronic Ulcers	

If the ulcer healed status is missing at a particular assessment and the ulcer was marked as healed at the previous assessment then the ulcer should be classified as healed.

If the ulcer healed status is missing at a particular assessment and the ulcer was not marked as healed at the previous assessment then the ulcer should not be classified as healed. If the baseline ulcer healed status is missing then this should also be implemented as not healed.

In cases where the wound is recorded as healed in the investigators opinion the following imputations will be made if missing values are present: Signs of critical colonisation or infection = No. Level of Exudate = None.

Healthcare resource use

If any of the healthcare resource data is missing then no missing data implementation will be used.

Dressing Change

If any of the dressing change data from the exploratory endpoints is missing then no missing data implementation will be used.

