- Ulcer length/width/depth will be used to derive area and volume. These variables will then be used to derive the reduction in area, depth, and volume from baseline to three, six and twelve weeks. The reduction in each dimension at each assessment (3, 6 and 12 weeks) will be analysed as the dependent variable in separate ANCOVA models. As a minimum the models will contain a term for treatment. The following terms will be added to the model using a stepwise selection procedure with an F-value to attain a significance level of 0.1: centre, subject, wound type, BMI and the relevant baseline wound dimension (area/ depth/ volume). The estimate difference in the LSMean reductions from baseline in area, depth, and volume (separately) between treatments will be presented with the associated 95% confidence interval.
- Reference ulcer healed (100% re-epithelialized, no drainage, no need for a dressing) will be summarized at each assessment (at three, six, and twelve weeks) and analyzed using a repeated measures logistic regression model with whether the reference ulcer was healed or not at the assessment as the dependent variable. As a minimum the model will contain a term for treatment. The following terms will be added to the model using a stepwise selection procedure with an F-value to attain a significance level of 0.1: centre, wound type and BMI..

Healthcare resource use

CONFIDENTIAL AND PROPRIETARY

This document contains information that is confidential and proprietary to Smith & Nephew PLC and Smith & Nephew, Inc. and is intended for use only by Smith & Nephew and its manufacturer. It shall not be reproduced or copied in whole or in part, nor shall the contents be disclosed by any means without prior written permission from Smith & Nephew, nor shall anyone make any use of it that is contrary to the expressed or implied wishes of Smith & Nephew

Statistical Analysis Plan	
A Pilot Randomized Controlled Trial to Evaluate an Advanced Borderless Dressing (ALLEVYN™ LIFE Non-Bordered) in the Treatment of Chronic Ulcers	Number: CT1603ALF
	ST: 1005
	Version: 1.0, 27-Jul-2018
	Page: 24 of 27

The following Healthcare resource variables will be summarized by treatment groups and overall (i.e. all assessments together) using continuous or categorical data summaries (as appropriate):

- Number and type of dressings used (both primary and secondary dressings), including use of compression therapy
- Number of outpatient visits

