7.12 Analysis of Exploratory Endpoints

- The average dressing wear time (days) per subject will be calculated and this will be summarized as a continuous variable by treatment group and overall. An estimate of the difference in wear time between treatment groups will be reported with the corresponding 95% confidence interval at twelve weeks only.
- Dressing leakage will be summarized by treatment group and overall
- Ease of dressing application/removal will be summarized by treatment group and overall
- Dressing use (whether dressing was cut and adherence following repositioning) will be summarized by treatment group and overall
- Durafiber/ Intrasite use will be summarised
- Odor control of dressing will be summarized by treatment group and overall
- Absorption of exudate under compression will be summarized by treatment group and overall.
- Reason for dressing change will be summarized by treatment group and overall

CONFIDENTIAL AND PROPRIETARY

This document contains information that is confidential and proprietary to Smith & Nephew PLC and Smith & Nephew, Inc. and is intended for use only by Smith & Nephew and its manufacturer. It shall not be reproduced or copied in whole or in part, nor shall the contents be disclosed by any means without prior written permission from Smith & Nephew, nor shall anyone make any use of it that is contrary to the expressed or implied wishes of Smith & Nephew

Statistical Analysis Plan	 Number: CT1603ALF ST: 1005 Version: 1.0, 27-Jul-2018 Page: 25 of 27
A Pilot Randomized Controlled Trial to Evaluate an Advanced Borderless Dressing (ALLEVYN™ LIFE Non-Bordered) in the Treatment of Chronic Ulcers	

- Pain on dressing removal will be summarized by treatment group and overall and an estimate of the difference between treatment groups will be reported with the corresponding 95% confidence interval.
- Comfort during wear will be summarized by treatment group and overall

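### Healthcare resource use is a between-group secondary endpoint, but the analysis sections plan only by-arm and overall summaries, with no ALNB - SC difference or interval

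*SAP*

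**What the plan says.** **A comparison is promised.** SAP section 3 (and Protocol 8.1) says: "Health care resource use data will be gathered and compared over the entire twelve week study period". SAP 5.3 (and the Protocol synopsis) lists "Healthcare resource use variables (to be compared between groups over the entire twelve week study period) including" dressings, consultations, provider time, hospital nights, procedures and concomitant treatments. Protocol 8.2 adds that the study seeks to estimate the effects of ALNB on resource use. The opening of Protocol 10.2.2, which covers all secondary variables, says they will be assessed for differences between arms and leaves details to the SAP.

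**Only summaries are specified.** Protocol 10.2.2.2: "The following Healthcare resource variables will be summarized by treatment groups and overall at twelve weeks". SAP 7.11: "The following Healthcare resource variables will be summarized by treatment groups and overall (i.e. all assessments together) using continuous or categorical data summaries". Both lists contain dressings, outpatient visits, hospital nights, procedures and concomitant treatments. Neither contains provider time. SAP 7.4 derives no resource-use total, and SAP 7.15 records no decision to drop the comparison. For missing resource data, SAP 7.3 says: "If any of the healthcare resource data is missing then no missing data implementation will be used".

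**Elsewhere a contrast is named.** For wear time, an exploratory variable, SAP 7.12 says: "An estimate of the difference in wear time between treatment groups will be reported with the corresponding 95% confidence interval at twelve weeks only". The same section plans a difference with an interval for pain on dressing removal.

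**The concern.** The protocol defers the method of a secondary comparison to the SAP, and the SAP supplies none: no contrast, estimator or interval. A listed secondary endpoint is therefore analysed less fully than two exploratory ones.

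The pilot's stated aim includes preliminary health-economic data to help plan cost-effectiveness research. Someone planning that research needs the size of the difference and how uncertain it is. Two columns of summaries on 25 and 15 subjects, probably with skewed counts, leave readers to judge by eye whether a gap between arms exceeds chance variation.

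**Working it through.** **1. Design figures.** SAP 6.1 wants 25 ALNB subjects at 5:3. That gives 25 x 8/5 = 40 in total and 25 x 3/5 = 15 on SC, which agrees with the stated sample size. The documents give no SD, effect size or precision target for resource use.

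**2. What is planned for each type of endpoint.**

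| Endpoint | Tier | Planned output |
|---|---|---|
| Bates-Jensen total | secondary | LS mean difference, 95% CI |
| Area, depth, volume reduction | secondary | LS mean difference, 95% CI |
| Healed status | secondary | logistic regression |
| Peri-wound condition | secondary | cross-tabulation only |
| **Resource use** | **secondary** | **summaries only** |
| Wear time, removal pain | exploratory | difference, 95% CI |
| Leakage, ease, odor, absorption, reason for change, comfort | exploratory | summaries only |

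Resource use is not the only summary-only item. It is, however, the one that Protocol 8.2 names as an effect to be estimated and that the study design sections single out for comparison.

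**3. What a reader could recover from the planned tables.** SAP 7.1 requires n, mean, median, SD, minimum and maximum for continuous summaries. If the table is built on one total per subject, a crude standard error is sqrt(s1^2/n1 + s2^2/n2). SAP 7.11 does not say that it is, and its description of overall as all assessments together leaves the unit open.

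**4. Precision of the missing estimate.** With a common SD:
- SE = SD x sqrt(1/25 + 1/15) = 0.3266 SD.
- 95% half-width = t(0.975, 38 df) x SE = 2.024 x 0.3266 SD = 0.66 SD.
- With fewer analysed subjects (assumed numbers): 0.71 SD at 22 vs 13, and 0.75 SD at 20 vs 12.

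In dressings over twelve weeks, with the SD assumed:

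| Assumed SD | SE | 95% half-width |
|---|---|---|
| 5 | 1.63 | 3.3 |
| 10 | 3.27 | 6.6 |
| 15 | 4.90 | 9.9 |

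**5. Which estimator is workable.**
- Outpatient visits are partly set by the protocol: at least one per week (8.1), with all dressing changes on site (6.2.2). The counts may vary less than a Poisson variable, which a negative binomial model cannot represent.
- Protocol 7.1 allows as few as 3 SC subjects per ulcer type. Bootstrapping within a cell of 3 understates the standard error of that cell's mean by a factor of sqrt(2/3) = 0.82, or about 18%. Resampling should therefore be within arm only.
- If nobody in an arm has an event (hospital nights, for example), that arm adds no bootstrap variability and the interval looks falsely narrow.

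**The case against.** The strongest case is that side-by-side summaries are a legitimate form of comparison in a feasibility-sized pilot. Protocol 5.6 says significant differences are unlikely, SAP 7.8 disclaims confirmatory intent, and the synopsis lists resource use apart from the objectives introduced as effects to be estimated. Other items said to be compared, such as peri-wound condition and leakage, are also only summarised. SAP 7.1 adds that "95% two-sided confidence intervals will be generated where appropriate", and the table shells, which might show more, are not available.

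Much of this stands, and it rules out three stronger readings that a reader might infer:
- *No comparison is made at all, or only bare means are shown.* SAP 7.1 requires n and SD, so an informal contrast is possible.
- *The omission is unique to resource use.* The table above shows that it is not.
- *The tables are meant to support resource-use claims.* The key product claims that Protocol 8.2 names concern fluid handling and leakage, pain, comfort and odor.

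What does not stand is that nothing is missing. Pilot status excuses the absence of testing, not of an estimate, since estimation is the pilot's purpose. The general sentence in SAP 7.1 assigns no interval to any resource variable, and where the SAP wants one it says so. Rewording the plan to say summarised would remove the mismatch in terms, but it would leave the effect estimate named in Protocol 8.2 undelivered.

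**Conclusion.** The point holds as a gap between a stated secondary comparison and its analysis. The plan provides by-arm descriptions from which an informal contrast can be drawn, but reports no ALNB - SC difference or interval for any resource variable and omits provider time, a listed endpoint, from the analysis list.

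The missing intervals would be wide, about +/-0.66 SD at 25 vs 15. That figure assumes a common SD, complete totals and an approximately valid t interval. The values in dressings depend on assumed SDs of 5 to 15. The primary endpoint is unaffected, so this is worth correcting but does not threaten the trial's main result.

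The correction does not yield a cost comparison. The objective in SAP 4.3 covers "number and cost of dressings used, consultations and time used by healthcare professionals (HCP), time in hospital", but no cost variable is listed as an endpoint or derived. That is a separate gap.

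**What to change.** In SAP 7.11 keep the summaries and add, for each per-subject twelve-week total, the ALNB - SC difference in means with a 95% confidence interval and no p-value. The totals are primary dressings, secondary dressings, outpatient visits, hospital nights, procedures, concomitant treatments, and the visit time already recorded under Protocol 9.2 (as the measure of provider time). Define each total in SAP 7.4.

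- **Interval:** name one simple robust method in advance, either a bootstrap resampled within arm only or an unequal-variance t interval.
- **No events in an arm:** report the counts only, without a bootstrap interval.
- **Shortened follow-up:** state how these subjects are counted. Separate those whose use ended because the ulcer closed from those who left the study or stopped treatment. Protocol 9.2.4 says follow-up after treatment ends is mainly for CWIS and adverse events, so later resource use may not be fully recorded.

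The cost is SAP wording and a few extra outputs, with no new data collection. The downside is wide intervals, and outpatient visit differences will need a note that the minimum frequency is set by the protocol.
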